## 4.4 Entry Criteria

The following eligibility criteria were designed to select patients for whom the protocol treatment is considered appropriate. All relevant medical and non-medical conditions should be taken into consideration when deciding whether this protocol is suitable for a particular patient. Eligibility criteria may not be waived by the investigator.

### 4.4.1 Inclusion criteria

In order to be eligible for participation in this trial, the patient must:

1. Patients should be  $\geq 18$  years old on the day of signing the informed consent.
2. Patients must have a histological or cytological diagnosis of NSCLC.
3. Patients should have non-radically treatable stage IIIB or IV disease.
4. Patients must have measurable disease as assessed by RECIST v1.1.
5. Patients must have had disease progression or be intolerant of standard first line palliative chemotherapy for non-small cell lung cancer. If they are known to have a driver mutation for which there is a small molecule targeted therapy, they must have had disease progression or be intolerant of this.
6. Patient should have an ECOG performance status 0-1.
7. Patients should be able to tolerate a course of stereotactic radiotherapy as assessed by the investigator.
8. Patients should have disease within the lung, away from critical structures, suitable for treatment to part of a lesion with lung SBRT.
9. Patients must have adequate organ function including MRC dyspnoea score  $<3$  and adequate baseline lung function tests, with an  $FEV_1 > 0.8L$  or  $>30\%$  of predicted and a  $TLCO > 30\%$
10. Demonstrate adequate organ function as detailed in Table 2 (based on bloods within 10 days of C1D1).
11. Have provided tissue from an archival tissue sample or newly obtained tissue sample.
12. Female patient of childbearing potential should have a negative urine or serum pregnancy within 72 hours prior to receiving the first dose of study medication (C1D1). If the urine test is positive or cannot be confirmed as negative, a serum pregnancy test will be required.
13. Female patients of childbearing potential should be willing to use 2 methods of birth control or be surgically sterile, or abstain from heterosexual activity for the course of the study through 120 days

after the last dose of study medication. Patients of childbearing potential are those who have not been surgically sterilized or have not been free from menses for > 1 year.

14. Male patients should agree to use an adequate method of contraception starting with the first dose of study therapy through 120 days after the last dose of study therapy.
15. Be willing to provide informed consent for the trial.

**Table 2:** Adequate Organ Function Laboratory Values. These should be within 10 days of C1D1.

System	Laboratory Value
Haematological	
• Absolute neutrophil count (ANC)	$\geq 1.5 \times 10^9/L$
• Platelets	$100 \times 10^9/L$
• Haemoglobin	$\geq 90 \text{ g/L}$ or $\geq 5.6 \text{ mmol/L}$
Renal	
• Serum creatinine OR • Measured or calculated a creatinine clearance (GFR can also be used in place of creatinine or CrCl)	$\leq 1.5 \times$ upper limit of normal (ULN) OR $\geq 60 \text{ mL/min}$ for patient with creatinine levels $> 1.5 \times$ institutional ULN
a Creatinine clearance should be calculated per institutional standard.	
Hepatic	
• Serum total bilirubin OR • Direct bilirubin	$\leq 1.5 \times$ ULN OR $\leq$ ULN for patients with total bilirubin levels $> 1.5 \text{ ULN}$
• AST (SGOT) and ALT (SGPT)	$\leq 3.0 \times$ ULN OR $\leq 5.0 \times$ ULN for patients with liver metastases
Coagulation	
Prothrombin Time (PT)	$\leq 1.5 \times$ ULN unless patient is receiving anticoagulant therapy as long as PT or PTT is within therapeutic range of intended use of anticoagulants
Activated Partial Thromboplastin Time (aPTT)	$\leq 1.5 \times$ ULN unless patient is receiving anticoagulant therapy as long as PT or PTT is within therapeutic range of intended use of anticoagulants

#### 4.4.2 Exclusion Criteria

The following patients must be excluded from participating in the trial:

1. Patients who have taken any investigational medicinal product or have used an investigational device within 4 weeks of the first dose of pembrolizumab. Patients may participate in additional observational studies.
2. Patients who have received prior chemotherapy, targeted small molecule therapy or radiotherapy within 4 weeks prior to the first dose of pembrolizumab.
3. Patients with a diagnosis of immunodeficiency or be receiving systemic steroid therapy ( $>7.5 \text{ mg of prednisone} / >1 \text{ mg of dexamethasone or their equivalent dose}$ ) or any other form of immunosuppressive therapy within 7 days prior to the first dose.
4. Patients with evidence of active autoimmune disease requiring systemic treatment within the past 3 months or a documented history of clinically severe autoimmune disease, or a syndrome that requires systemic steroids or immunosuppressive agents.
5. Patients who have received prior therapy with an anti-PD-1, anti-PD-L1, anti-PD-L2, anti-CD137, or anti-Cytotoxic T-lymphocyte-associated antigen-4 (CTLA-4) antibody (including ipilimumab or any other antibody or drug specifically targeting T-cell co-stimulation or checkpoint pathways).

6. Patients with evidence of active central nervous system (CNS) metastases and/or carcinomatous meningitis. Patients with previously treated brain metastases may participate provided the brain metastases are stable and there is no evidence of new or enlarging brain metastases.
7. Patients who have had previous radiotherapy to the lung or other neighbouring region that would preclude the safe administration of lung SBRT.
8. Patients with evidence of interstitial lung disease, or history of pneumonitis (including non-infectious pneumonitis) that required steroids, or current pneumonitis (including non-infectious pneumonitis).
9. Patients with evidence of additional malignancy that is progressing or requires active treatment.
10. Patients with a history or current evidence of any condition, therapy, or laboratory abnormality that might confound trial results, interfere with the patient's participation or is not in the best interest of the patient.
11. Patients with psychiatric or substance abuse disorders that would interfere with patient's participation.
12. Patients who are pregnant / breastfeeding or expecting to conceive within the duration of the trial, starting with the screening visit through 120 days after the last dose.
13. Patients with a history of HIV, HIV 1/2 antibodies, Hepatitis B or Hepatitis C.
14. Patients who have received a live vaccine within 30 days prior to the first dose of trial treatment.
15. Patients with known hypersensitivity to the active substance pembrolizumab or to any of the excipients listed in the SmPC.

## 5 STUDY PLAN AND PROCEDURES

---

### 5.1 Study Schedule

From study entry, patients will be assessed every 21 days, prior to the administration of each dose of pembrolizumab. During the week of lung SBRT patients will have an additional clinical review. Patients will continue to be assessed and stay on Pembrolizumab until they have disease progression, suffer unacceptable toxicities, withdraw the study ends or have completed 24 months of pembrolizumab. Treatment beyond progression or beyond 24 months needs to be discussed with the study sponsor and MSD. Patients will be required to attend a safety visit 30 days after their last dose of Pembrolizumab.

If the patient has not progressed at the last dose of pembrolizumab they will be reviewed every 9 weeks until the start of new anti-cancer therapy, disease progression, death, withdrawal or end of the study. Patients that have progressed or begin a new anti-cancer treatment will enter into the survival follow up phase and an update will be sought every 12 weeks to assess for disease status until death, withdrawal of consent, or the end of the study, whichever occurs first. Survival follow up can be done over the phone.

The schedule of assessments to be performed at each visit is summarised in Table 3. Individual trial procedures are described in detail below. It may be necessary to perform these procedures at unscheduled time points if deemed clinically necessary by the Investigator. Furthermore, additional evaluations/testing may be clinically indicated for reasons related to patient safety. In some cases, such evaluation/testing may be potentially sensitive in nature (e.g., HIV, Hepatitis B, Hepatitis C, etc.) and will be performed in accordance with local regulations.

**Table 3:** Study Schedule of Assessments

Trial Phase:	Screening period	Dose escalation phase			Maintenance phase DLT period (Pembrolizumab 200 mg q3wkly)			Maintenance phase Beyond DLT period (Pembrolizumab 200 mg q3wkly)			End of Treatment (If applicable)	Post-Treatment				
		C1, D1	Radiotherapy phase (30 Gy in 3# OR 54 Gy in 3#)									Safety Follow-up (SFU)	Follow Up Visits	Survival Follow Up		
Treatment Cycle/Title:			C1, D15	C1, D17	C1, D19	Discontinuation of Pembrolizumab	30 days after last dose					Every 9 weeks from SFU	Every 12 weeks from SFU			
Scheduling (Day):	-28 to -1					±3	±3	±3	±3	±3	±3	±7	±7	±7	±7	
Informed Consent	X															
Inclusion/Exclusion	X															
Clinical history	X															
Full Physical Exam	X	X										X	X			
Directed Phys. Exam			X	X	X	X	X	X	X	X	X					
Adverse Events	X	X	X	X	X	X	X	X	X	X	X	X	X	X		
MRC dyspnea score	X		X	X	X	X	X	X					X			
Medications	X	X	X	X	X	X	X	X	X	X	X	X	X	X		
ECOG PS	X	X	X	X	X	X	X	X	X	X	X	X	X	X		
Vital Signs & Weight	X	X	X			X	X	X	X	X	X	X	X	X		
Height	X															
Haem & Biochem	X 	X 				X 	X 	X 	X 	X 	X 	X 	X	X		
FT3, FT4 and TSH	X 	X					X		X		X		X	X	X	
PT and aPTT	X 															
Pregnancy Test	X 															
Urinalysis	X 															
Pembrolizumab		X				X	X	X	X	X	X	X				
Radiotherapy			X 	X 	X 											
Pulmonary function 	X											X				
Imaging	CT  & CXR 					CXR	CXR	CXR	CT	CXR		CT		CT	CT	
PD-L1 assessment 	X															
Research Blood		X				X			X				X			
Survival Status															X	

1. Imaging with a CT scan should occur during the screening period as a baseline and then every 9 weeks (3 cycles) for the first 6 months, then every 12 weeks after 6 months (regardless of treatment delays). Imaging with CT scanning can occur 7 days before the visit to ensure that the results are available at the visit.
2. Chest x-ray will be performed during the dose limiting toxicity period in order to monitor for pneumonitis.
3. Full pulmonary function tests should be performed every 6 months from radiotherapy.
4. Dose escalation and expansion cohort will not be enriched for PD-L1 strong patients. PD-L1 testing will be batched and performed once all patients are on study.
5. Lung SBRT will be administered at dose level being tested on C1D15, C1D17 and C1D19 during the dose escalation phase, and at the RP2D for C1D15, C1D17 and C1D19 during the dose expansion phase.
6. Screening laboratory investigations will be valid for 10 days from C1D1.
7. Safety laboratory investigations will be valid for 3 days from D1 visit.

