#### 3.2 Treatment Regimen

The study will be conducted in two parts; an initial lung SBRT dose escalation phase (Part A), followed by a lung SBRT dose expansion cohort (Part B). The dose escalation phase is based on a 3+3 design such that patients will be treated in cohorts of 3-6 patients. A maximum of 12 patients will be allocated to one of two doses of lung SBRT in combination with pembrolizumab to determine the MTD, DLTs and RP2D. If there is more than one DLT in cohort 1, this treatment combination will be deemed as being unacceptable, and it would lead to termination of the study. Note, there is no de-escalation in cohort 1. During the dose expansion cohort, 12 patients will have lung SBRT dosed at the RP2D determined during the dose escalation phase in combination with pembrolizumab to obtain additional safety and response data. Maintenance pembrolizumab will continue until disease progression, unacceptable toxicities, the patient withdraws consent to the trial, or the patient has completed 24 months of treatment. A maximum of 24 patients will be treated in the study.

All patients will receive pembrolizumab on cycle (C) 1 day (D) 1, in Part A and B of the study. All patients will receive lung SBRT on C1D15, C1D17, and C1D19 as per lung SBRT protocol (See Appendix 3). Although C1D1 can occur +/- 3 days, C1D15, C1D17, and C1D19, must be scheduled for a Monday, Wednesday and Friday, respectively. Patients in part A will receive lung SBRT dosed at 30 Gy in 3# in cohort 1, or 54 Gy in 3# in cohort 2. Patients in Part B will receive the RP2D of lung SBRT, determined in Part A. All patients in Part A and Part B will receive pembrolizumab dosed at 200 mg every 3 weeks, until disease progression, unacceptable toxicities, the patient withdraws consent from the trial, or the patient has completed 24 months of treatment.

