In the dose escalation phase, a minimum of 3 patients will be required per dose level being assessed. A minimum gap of 1 week will be left between the treatment of the first and the second, and between the second and the third patients with the combination of pembrolizumab and lung SBRT to mitigate against multiple patients suffering from acute toxicity. The DLT period for this study is 12 weeks from the last dose of lung SBRT (i.e. at C6D1). The dose escalation will be considered by the Safety Review Committee (SRC) once the 3rd or 6th patient in the cohort has completed the DLT period. If no DLT is observed at a dose level,

then lung SBRT will be dose escalated to the next dosing level (see Table 1). If 1 out of 3 patients experience a DLT, then the cohort will be expanded to 6 patients. If 1 in 6 patients experience a DLT, then the dose will be escalated to the next dosing level. However, if  $\geq 2$  in 6 patients experience a DLT then the maximum administered dose (MAD) will have been reached, and the RP2D will be the previous dosing level that will be used for the dose expansion cohorts. If the MAD is seen at dose level 1 then the study will be terminated. While waiting for 3 or 6 patients to complete the DLT period, no additional patients will be recruited. Further patients can only be recruited after the SRC has reviewed the toxicity data for the cohort and taken a decision to dose escalate to the next cohort or expand the current cohort to 6 patients.

Once the MTD has been determined the trial enters the dose expansion phase (unless the MTD is dose level 1). Here, 12 patients will be treated with the RP2D of SBRT combined with pembrolizumab.

If there is ongoing clinical benefit at 24 months, the CI/PI will need to discuss with the sponsor and MSD, on a case by case basis for the continuation of pembrolizumab.

**Table 1:** Lung SBRT dose levels and pembrolizumab dosing during the dose escalation and dose expansion phase.

Dose Level	Pembrolizumab Dose	Lung SBRT to part of a lung lesion
1	200 mg i.v. over 30 minutes, every 3 weeks	30 Gy in 3# (Monday, Wednesday, Friday)
2	200 mg i.v. over 30 minutes, every 3 weeks	54 Gy in 3# (Monday, Wednesday, Friday)
Dose expansion	200 mg i.v. over 30 minutes, every 3 weeks	RP2D

SBRT: Stereotactic Ablative Body Radiotherapy; Gy: Gray; i.v.: intravenous; mg: milligrams;  
RP2D: Recommended Phase 2 Dose; #: fraction.

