## **Non-Haematologic:**

Any NCI CTCAE  $\geq 3$  grade non-haematological toxicity that is definitely, probably or possibly related to the combination of pembrolizumab and lung SBRT including the following:

[figure not shown]
- Increased MRC dyspnoea score  $> 2$  grades from baseline and/or acute dyspnoea grade  $\geq 4$  (or CTCAE dyspnoea grade  $\geq 3$ ) persisting for  $> 7$  days (including weekend).
- Pneumonitis/pulmonary infiltrates grade  $\geq 3$  persisting for  $> 7$  days (including weekend).
- Oesophagitis grade  $\geq 3$  persisting for  $> 7$  days (including weekend).
- Toxicity leading to interruption of radiotherapy for  $> 7$  days (including weekend).

Escalation to the next dose level will not proceed until the following criteria are satisfied by the SRC:

- If 0 out of 3 patients experience a DLT, escalation to the next dose level can proceed.
- If 1 out of 3 patients experiences a DLT, a further 3 patients will be recruited at that dose level.
  - If 1 out of 6 patients experiences a DLT, then escalation to the next dose level can proceed.
  - If  $\geq 2$  out of 6 patients experience a DLT, the MAD will have been reached. The RP2D will be the dose level prior to when the DLTs were observed or dose level 2 if no DLTs were observed.  
All patients in the expansion cohort will have lung SBRT dosed at the RP2D (see Figure 1).
- If 2/3 patients experience a DLT then the MAD will have been reached and the expansion cohort phase will begin at the previous dose level unless this occurs at dose level 1.
- If dose level 1 is not tolerated due to DLTs, the expansion cohort will not go ahead and the trial will be terminated.

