### **5.3.3 MRC dyspnoea Score**

The investigator or qualified designee will assess the patient's dyspnoea using the MRC Dyspnoea Score (Appendix 2) at screening period and the time points defined in the study schedule of assessments (Table 3).

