### **5.3.8 Pulmonary Function Tests**

Full lung function tests assessments will be performed at screening, prior to the dosing of pembrolizumab (+/- 5 days) and during the maintenance phase of the DLT period as specified in the study schedule of assessments (Table 3).

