### **8.1.4 Timing of analyses**

Toxicity data will be reviewed by the Safety Review Committee prior to any decision regarding dose escalation or opening of new dose cohorts.

Part A can be analysed once the last patient in cohort 2 has completed the DLT period which is 12 weeks from the last dose of lung SBRT (i.e. at C6D1). For parts A and B, end of treatment is until disease progression, or unacceptable toxicities, or the patient withdraws consent to the trial or when patient has completed 24 months of treatment. End of study is when the last patient has completed the off-study or the final follow-up visit, whichever happens last.

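### Table 3 schedules no MRC dyspnoea score at C5D1 or C6D1, so the MRC limb of the dyspnoea DLT has no planned assessment for about 46–48% of the DLT window

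*Combined protocol and SAP*

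**What the plan says.** - **The criterion.** The non-haematological list in Section 3.2.1 has a dyspnoea item that opens "Increased MRC dyspnoea score". It is met by a rise of more than 2 grades from baseline and/or acute dyspnoea of grade 4 or more, with CTCAE dyspnoea of grade 3 or more as an alternative, persisting for more than 7 days. The toxicity must be at least possibly related to the combination.
- **The window.** Section 3.2: "The DLT period for this study is 12 weeks from the last dose of lung SBRT (i.e. at C6D1"). Section 8.1.4 repeats it: "DLT period which is 12 weeks from the last dose of lung SBRT (i.e. at C6D1"). Section 3.2.1 also takes acute toxicity assessment up to and including that visit.
- **Timing of the score.** Section 5.3.3 has it taken "at screening period and the time points defined in the study schedule of assessments (Table 3"). It names no other visits.
- **The schedule.** In Table 3 the row "MRC dyspnea score" is ticked at screening, C1D15, C1D17, C1D19 and the three visits that follow. The next four columns are blank, and there is one further tick in a post-treatment column.
- **Chest imaging.** Footnote 2 of Table 3: "Chest x-ray will be performed during the dose limiting toxicity period in order to monitor for pneumonitis".

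**The concern.** A DLT criterion that depends on a measured change from baseline can be applied only where the measurement is taken. If the score stops part-way through the window, the patient reaches C6D1, when the DLT period closes and the Safety Review Committee can consider escalation, with no current MRC value.

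The primary endpoint is the MTD and RP2D, decided on 3 to 6 patients per level. Under the rules of Section 3.2.1, one unrecorded DLT turns 1/3 (enrol three more) into 0/3 (escalate), or 2/6 (maximum administered dose reached, and termination if at dose level 1) into 1/6 (escalation allowed). An unrecorded event can only make a dose look safer than it is.

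**Working it through.** **1. Which visits the columns are.** The cycle labels after C1D19 are lost in the extracted Table 3, so I counted cells from the left, with screening as column 1.

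| Row | Columns filled | What it shows |
|---|---|---|
| Radiotherapy | 3, 4, 5 | C1D15, C1D17, C1D19 |
| Pembrolizumab | 2, 6–12 | column 6 is the first dose after C1D1 |
| Research blood | 2, 6, 9, 13 | Section 5.3.13 names C1D1, C2D1, C5D1 and end of study |
| Thyroid tests (on treatment) | 2, 7, 9, 11 | fits C1, C3, C5, C7 |
| Chest imaging | X-ray 6, 7, 8, 10; CT 9 | X-ray, a DLT-period test, is still done in column 10 |
| Adverse events | 1–14 | no gap in the window |
| MRC score | 1, 3–8, 13 | blank in 9–12 |

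Column 6 is therefore C2D1, column 8 is C4D1, column 9 is C5D1 and column 10 is C6D1. The last on-treatment MRC score is at C4D1.

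**2. The plan's own window.** Section 3.2 states "All patients will receive lung SBRT on C1D15, C1D17, and C1D19", so the last fraction is on day 19. Visits are every 21 days, so CnD1 = 1 + 21(n − 1).
- C4D1 = 1 + 63 = day 64; C5D1 = 1 + 84 = day 85; C6D1 = 1 + 105 = day 106.
- Twelve weeks from the last fraction = 19 + 84 = day 103. C6D1 is 106 − 19 = 87 days after it (12.4 weeks), and its ±3-day allowance reaches day 103. The plan's equation of 12 weeks with C6D1 is reproduced to within that allowance.

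**3. The part without a scheduled score.**
- Strict 12 weeks: 103 − 64 = 39 of 84 days = 46%.
- To C6D1: 106 − 64 = 42 of 87 days = 48%.
- With C4D1 moved by ±3 days: from (103 − 67)/84 = 43% to (106 − 61)/87 = 52%.
- By visits: C2D1 to C6D1 is five post-radiotherapy cycle visits, of which three have a score.

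**4. What depends on the MRC score alone.** Inclusion criterion 9 requires MRC below 3, so baseline is 0, 1 or 2. A rise of more than 2 grades on the 0–5 scale of Appendix 2 means 0 to 3 or worse, 1 to 4 or worse, or 2 to 5. MRC 4 is illustrated by breathlessness on undressing, and MRC 5 is breathlessness at rest. Appendix 4 counts undressing as self-care, and limitation of self-care as grade 3, so rises ending at 4 or 5 should normally also meet the CTCAE alternative. A rise from 0 to 3 (breathless within 100 yards) need not limit self-care. That is the case that rests on the score.

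**The case against.** **The column reading is inferred.** This is fair as a caution. The header gives the dose-escalation block three cells for four visits, so its spans are not reliable. The CT column also looks awkward: nine weeks counted from C1D1 is day 64 (C4D1), whereas the CT sits in the column read here as C5D1. That does not move the columns. Column 6 is the first visit after C1D19, and nine weeks from the last fraction is 19 + 63 = day 82, within 7 days of C5D1 (day 85). The original table should still be checked.

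**The header may limit the DLT period to three cycles.** As extracted, the maintenance block labelled as the DLT period spans three cells, and the MRC row has exactly three maintenance ticks. The row may simply follow that label. If so, the header conflicts with C6D1 in Sections 3.2, 3.2.1 and 8.1.4, and with the table's own chest X-ray in column 10. The conflict remains, but in a different place.

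**Other text covers the gap.** Section 6.1.2 says a dyspnoea score will be recorded, Section 3.2.1 uses the MRC score at baseline and on treatment, and Section 5.1 allows unscheduled procedures if the investigator thinks them clinically necessary. None of these requires an MRC score at C5D1 or C6D1. A patient who stops treatment early might have the post-treatment score inside the window.

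**CTCAE grading is a backstop.** This objection carries the most weight. A reader might infer that respiratory DLTs as a whole go unmeasured in the second half of the window. The documents do not support that. Adverse events are reviewed at every visit, CTCAE dyspnoea of grade 3 or more satisfies the same item, and pneumonitis of grade 3 or more persisting over 7 days is a separate DLT. What is left is the narrow case in step 4 of the working: related to treatment, arising after C4D1, lasting over 7 days, below CTCAE grade 3, and not prompting an unscheduled score.

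**Conclusion.** The point holds for the MRC limb only. A measure that the protocol made a DLT trigger has no scheduled assessment at two of the five post-radiotherapy cycle visits in the window, including the visit that closes it: 39 of 84 to 42 of 87 days (46–48%; 43–52% allowing for the visit window at C4D1).

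This rests on three assumptions: that the column reading matches the original Table 3, that C6D1 is the intended end of the DLT period, and that visits fall on their nominal days apart from the allowance shown.

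It would be going too far to say that DLTs will be missed or that the MTD/RP2D is biased upward. The documents give no rate for the 0-to-3 rise, so the probability of a miss cannot be computed. What can be said is that such a DLT could be missed, that the error would run in one direction, and that at 3 to 6 patients per level a single one could change the decision. The correction is worth making because it costs almost nothing.

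**What to change.** 1. In Table 3, add the MRC dyspnoea score at C5D1 and C6D1. Both visits already have a directed examination, adverse event review and chest imaging, so the cost is one clinician-rated item at each. Scheduled scores rise from three to all five post-radiotherapy cycle visits, and the longest interval without a score falls from 39–42 days to 21 days.
2. Reconcile the DLT-period header of Table 3 with the C6D1 end point in Sections 3.2, 3.2.1 and 8.1.4, after checking the original table. If the header does mean three cycles, the sponsor needs to state which end point applies and make all four places agree.
3. Separately, and minor because it is not a DLT criterion: Section 5.3.8 places lung function tests "during the maintenance phase of the DLT period as specified in the study schedule of assessments (Table 3"), but Table 3 ticks them only at screening and in column 12, beyond C6D1, and footnote 3 sets them every 6 months from radiotherapy. These should state the same time points.

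Items 2 and 3 need wording changes only.
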